2.3 STUDY TREATMENTS

Following procurement of informed consent and completion of baseline screening assessments, patients that meet all inclusion/exclusion criteria will be randomly assigned to receive one of the two following treatments, starting on Day 1, in a ratio of 2:1.

1.) EXPERIMENTAL BELIMUMAB TREATMENT (n=12). Subjects randomized to the experimental treatment arm will receive i.v. administrations of belimumab (10 mg/kg), consisting of three "loading" doses, two weeks apart, followed by five (5) more monthly infusions. The final assessment will be performed at month 7 (see Table 1).

2.) PLACEBO CONTROLS (n=6): These subjects will be treated with identically appearing placebo i.v. on the same schedule as the experimental arm subjects (i.e., three "loading" doses, two weeks apart, followed by five more monthly infusions. The final assessment will be performed at month 7 (see Table 1).

		Loadi	ng Doses]			
Days	1	14	30	60	90	120	150	180	210
Study	х	Х	х	Х	х	Х	Х	Х	Assessment
Drug									only (final)

Table 1. Schedule of study drug infusions (either belimumab or placebo) and final assessment

2.4 RANDOMIZATION

Randomization by random number generator and assignment to one of the two treatment arms will be effected by the Investigational Drug Service at UAB.

2.5. STUDY TREATMENT SCHEMATIC

The experimental interventions are outlined below in Table 2:

Study Day (month)	Screening*	1	14	30 (1)	60 (2)	90 (3)	120 (4)	150 (5)	180 (6)	210 (7)	240 (8)	300 (10)
Clinic Visit	x	x	x	x	x	x	x	x	x	x		χ [†]
Physical Exam	x	x	x	x	x	x	x	x	x	x		
Experimental Treatment		x	x	x	x	x	x	x	x			
Spirometry	X#			x		x		x		X#		
DLCO	x											
6 Minute Walk Test	x									x		

		1	1		1				1			1
Experimental Immunologic Assays	x			x		x		x		x		
Carotid Ultrasound	x									x		
lgA	x											
lgG	x			x	x	x	x	x	x	x		
Viruses [‡]	x											
CBC with platelets	x		x	x	x	x	x	x	x	x		
Basic Metabolic Panel	x		x	x	x	x	x	x	x	x		
Liver Function**	x		x	x	x	x	x	x	x	x		
Cotinine	x									x		
Autoimmune Serologies ^{††}	x											
Pregnancy Tests (if applicable)	x	x	x	x	x	x	x	x	x	x		\mathbf{x}^{\dagger}
Post-treatment Phone Checks		x	x	x	x	x	x	x	x		x	x

Table 2. Outline of Study Procedures and Tests. Notes: Telephone contacts will also be established on the days following experimental treatments (i.e., at day 2, 15, 31, 61, 91, 121, 151, and 181).

*Screening evaluations can occur over more than one day.

*Pre- & Post-bronchodilator Spirometry at screening and day 210 only, otherwise post- bronchodilator only

[†]Clinic visits and pregnancy tests at 10 months if applicable (female subjects with childbearing potential). Other subjects will have phone checks at 10 months.

[‡]Viruses include HIV, Hepatitis C antibody (HCAb), Hepatitis B surface antigen (HBsAg) and Hepatitis B core antibody (HBcAb)

**Routine liver function tests include alkaline phosphatase, total bilirubin, ALT, AST, and INR.

^{††}Autoimmune serologies are ANA, RF, anti-CCP, anti-SSA, anti-Jo-1

2.6 STUDY PROCEDURES

Routine clinical care for patients with pulmonary COPD will be followed as ordered by the primary physician.

All subjects will have infusions of study medications (belimumab or placebo) in an expert, dedicated, continuously-monitored UAB infusion center at the intervals delineated in Table 1. The treatment protocol will last for 180 days (6 months), with a final observation and specimen collection at day 210 (7 months) (see Table 1). Patients removed from the study for unacceptable AE will be followed until resolution or stabilization of the problem(s). Telephone interviews to detect potential late complications and outcomes will be conducted by study coordinators at other intervals (see Table 2).

Patients will be monitored carefully while participating in this study for occurrences of adverse events, laboratory test abnormalities, and changes in vital signs. Adverse events will be evaluated according to criteria outlined in the NCI Common Terminology Criteria for Adverse Events (CTCAE), version 4.0.

Belimumab will be administered IV over a minimum of 1 hour. The infusion rate may be slowed or interrupted if the subject develops an infusion reaction. In the event of a serious reaction, study agent administration must be discontinued immediately and the appropriate medical therapy administered.

In the post-marketing setting, delayed onset of symptoms of acute hypersensitivity reactions has been observed, especially in the first or second infusion. Subjects will remain under clinical supervision for 3 hours after completion of the first 2 infusions. Should symptoms of acute hypersensitivity occur, an extended period of monitoring may be appropriate, based on clinical judgement. This may include, but is not limited to, monitoring vital signs and observing any untoward reactions. Beyond the first 2 infusions, subjects should be monitored during infusion and for an appropriate period of time after infusion (this will generally be one hour, again based on investigator judgement).

Subjects should be made aware of the potential risk, the signs and symptoms of such reactions, and the importance of immediately seeking medical attention. For further information, see the belimumab IB.

Venous blood for experimental purposes (e.g., end-point measures), totaling 29 ml, and studyspecific pulmonary function tests (i.e., spirometry and diffusing capacities), will be obtained at screening (baseline) and at 1, 3, 5, and 7 months after treatment started (Table 2). Additional venous phlebotomy specimens for safety monitoring tests and assays appropriate for the experimental use of belimumab will be obtained at these and other intervals as needed (specified below).

The results of the pulmonary function tests, clinical data, and safety studies will be logged in case report forms (CRF) as they are generated (in real time). The experimental laboratory (immunological) assays will be performed intermittently among accumulated batched specimens and results recorded as they are performed.

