Funding Source:	GlaxoSmithKline (GSK)
Study Rationale:	This is intended to be an initial "proof-of-concept" study to show feasibility, validate assays and approaches, and explore dosing and safety of belimumab in pulmonary COPD patients who have clinically relevant (and quantifiable) autoimmune responses.
Study Objectives:	The primary goal of clinical trial is to determine effects of belimumab on levels of autoantibodies against glucose regulated protein 78 (GRP78) among patients with pulmonary COPD attributable to cigarette smoking.
Study Hypothesis:	Our study hypothesis is that belimumab treatment will safely reduce circulating levels of autoantibodies that are associated with COPD, and comorbidities of this lung disease, including atherosclerosis.

Study Aims:	 Specific Aim 1: To conduct a double-blind, Phase II trial, in which 18 former smokers with COPD and circulating anti-GRP78 autoantibody levels >mean normal values (by ELISA), will be randomized 2:1 to belimumab vs. placebo. Subjects will receive 8 infusions of either belimumab or placebo over a 6 month interval. Plasma anti-GRP78 antibodies will be measured pre-treatment, and at 1, 3, 5, and 7 months. We hypothesize belimumab therapy will more effectively reduce anti-GRP78 IgG autoantibodies, the primary endpoint of this trial, compared to placebo. Specific Aim 2: To determine effects of the belimumab therapy on secondary endpoints (at the times detailed for Aim 1) that include levels of pneumococcal-binding antibodies (by ELISA), circulating B-cell numbers and phenotypes (by flow cytometry), and the rate and severity of adverse events (AE) at any time during treatment. We hypothesize belimumab will have dose-related effects on B-cell numbers and their differentiation, while minimally reducing host defense antibodies, and will also have an acceptable AE profile.
Study Design:	Following baseline screening assessments, patients that meet all inclusion/exclusion criteria will be randomly assigned to receive one of the following treatments in a ratio of 2:1:
	1.) Arm 1: Belimumab (n = 12). Subjects randomized to the experimental treatment arm will receive i.v. administrations of belimumab (10 mg/kg), consisting of three "loading" doses, two weeks apart, followed by five (5) more monthly infusions. The final dose is administered at month 6 with final assessment at month 7 and a safety visit at month 10.

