	2.) Arm 2: Placebo Controls (n = 6) . These subjects will be treated with identically appearing placebo i.v. on the same schedule as the experimental arm subjects (i.e., three "loading" doses, two weeks apart, followed by five more monthly infusions. Again, the final assessment will be performed at month 7 ($210+10$ days after treatment start).
Planned Sample Size:	A total of 18 subjects will be enrolled in this trial. In order to reach the needed sample size of 18, twenty-five subjects will be randomized to account for subjects who have been withdrawn early due to the current COVID-19 pandemic in order to comply with guidance regarding human subjects research conduct and also for medical reasons un-related to study drug or study procedures.
Duration of Treatment:	Six months
Duration of Participation	Ten months
Inclusion Criteria:	 A history of past tobacco smoking (≥10 pack years), but quit for ≥6 months at the time of enrollment. Smoking cessation will be confirmed by serum cotinine assays.
	2.) Clinical diagnosis of at least moderate COPD as defined by the Global Initiative for Obstructive Lung Disease (GOLD) criteria:

	 a. Post bronchodilator FEV₁/FVC < 70%, b. Post bronchodilator FEV₁ between 25% and 80% predicted, with or without chronic symptoms (i.e., cough, sputum production). COPD
	3.) Ability and willingness to give informed consent.
	4.) Levels of plasma autoantibodies against a 15–mer peptide sequence within the GRP78 molecule (a.a. 246-260) that are in the upper three quartiles of values present in COPD patients. This epitope will henceforth be denoted as GRP78 Peptide 25. Levels of anti-GRP78 Peptide 25 autoantibodies are significantly correlated with carotid artery intimal medial thickness (IMT) among COPDpatients.
	5.) Age 40-75 y.o. COPD is a disease of older individuals.
Major Exclusion Criteria:	1.) History of more than one moderate (treated as outpatient) or severe (requiring hospitalization) acute exacerbation of COPD within the 12 months prior to screening or any moderate or severe exacerbation within the 4 months prior to screening. A past history of an acute exacerbation is the single biggest risk for recurrence. ³⁶ Exclusion of subjects at highest risk will minimize dropouts.
	2.) Oral steroids or cellular immunosuppressant use (e.g., cyclophosphamide) within 6 months.
	3.) History or clinical or laboratory evidence of other autoimmune syndromes (confirmed by self-report and medical record review).

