Complete abstinence from intercourse from 2 weeks prior to administration of the 1st dose of study agent until 16 weeks after the last dose of study agent (Sexual inactivity by abstinence must be consistent with the preferred and usual lifestyle of the subject. Periodic abstinence (e.g. calendar, ovulation, symptothermal, post-ovulation methods) and withdrawal are not acceptable methods of contraception)
OR
Consistent and correct use of 1 of the following acceptable methods of birth control for 1 month prior to the start of the study agent, during the study, and 16 weeks after the last dose of study agent:
 Oral contraceptive, either combined or progestogen alone
 Injectable progestogen
 Implants of levonorgestrel or etonogestrel
 Estrogenic vaginal ring
 Percutaneous contraceptive patches
 Intrauterine device (IUD) or intrauterine system (IUS) with <1% failure rate as stated in the product label

	 Male partner sterilization (vasectomy with documentation of azoospermia) prior to the female subject's entry into the study, and this male is the sole partner for that subject. For this definition, "documented" refers to the outcome of the investigator's/designee's medical examination of the subject or review of the subject's medical history for study eligibility, as obtained via a verbal interview with the subject or from the subject's medical records Double barrier method: condom and occlusive cap (diaphragm or cervical/vault caps) plus spermicidal agent (foam/gel/film/cream/suppository)
	21.) Use of Excluded Medications:
	Anti-B-cell therapy:
	 Wash out of 5 therapeutic half lives after prior B-cell therapy, or until pharmacodynamic effect would be minimal (e.g., 1 year following rituximab)
	365 days Prior to Belimumab:
	 Any biologic investigational agent (e.g., abetimus sodium, anti CD40L antibody, BG9588/ IDEC 131)
	 Investigational agent applies to any drug not approved for sale in the country in which it is being used
	• 30 Days Prior to Belimumab (or 5 half lives, whichever is greater)
	 Any non-biologic investigational agent
	 Investigational agent applies to any drug not approved for sale in the country in which it is being use
	 Live vaccines within 30 days prior to baseline or concurrently with belimumab
Study Endpoints:	Primary Endpoint : The primary endpoint of this trial is a reduction of circulating autoantibodies against the GRP78 epitope most correlated with carotid atherosclerosis.

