2.6.3 Other Variances

A variance of +/-5 days will be allowed for clinic visits and treatments, to account for weekends, holidays or other logistic problems. A variance of 10 days will be allowed for the surveillance visits on day 210, and day 300 (if applicable), for the same reasons.

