6.) History of malignant neoplasm within the last 5 years.

7.) Evidence of serious suicide risk including any history of suicidal behavior in the last 6 months and/or any suicidal ideation in the last 2 months or those, in the investigator's judgment, pose a significant suicide risk.

8.) History of a primary immunodeficiency.

9.) Significant IgG deficiency (IgG level < 400 mg/dL).

10.) Have an IgA deficiency (IgA level < 10 mg/dL).

11.) Currently on any suppressive therapy for a chronic infection (such as tuberculosis, pneumocystis, cytomegalovirus, herpes simplex virus, herpes zoster or atypical mycobacteria).

12.) Hospitalization for treatment of infection within 60 days of screening.

13.) Use of parenteral (IV or IM) antibiotics (antibacterials, antivirals, anti-fungals, or anti-parasitic agents) within 60 days of screening.

14.) Current drug or alcohol abuse or dependence, or a history of drug or alcohol abuse or dependence within 365 days prior to screening.

15.) History of a positive HIV test or positive screening test for HIV.

16.) Serologic evidence of current or past Hepatitis B (HB) or Hepatitis C (HC) infection based on positive tests for HBsAg or HBcAb, or HCAb.

17.) History of an anaphylactic reaction to parenteral administration of contrast agents, human or murine proteins or monoclonal antibodies.

18.) Any other clinically significant abnormal laboratory value in the opinion of the investigator.

19.) Any intercurrent significant medical or psychiatric illness that the investigator considers would make the candidate unsuitable for the study.

20.) Women of Child Bearing Potential (WCBP) must have a negative urine pregnancy test at screening, and agree to 1 of the following:

Complete abstinence from intercourse from 2 weeks prior to administration of the 1st dose of study agent until 16 weeks after the last dose of study agent (Sexual inactivity by abstinence must be consistent with the preferred and usual lifestyle of the subject. Periodic abstinence (e.g. calendar, ovulation, symptothermal, post-ovulation methods) and withdrawal are not acceptable methods of contraception)

OR

Consistent and correct use of 1 of the following acceptable methods of birth control for 1 month prior to the start of the study agent, during the study, and 16 weeks after the last dose of study agent:

- Oral contraceptive, either combined or progestogen alone
- Injectable progestogen
- Implants of levonorgestrel or etonogestrel

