5.6.3 Adverse Events Reporting Timeline

The investigators or site staff are responsible for detecting, documenting and reporting events that meet the definition of an AE or SAE. AEs will be collected from the start of study treatment and until the follow up contact. SAEs will be collected over the same time period as stated above for AEs. However, any SAEs assessed **as related** to study participation (e.g., study treatment, protocol-mandated procedures, invasive tests, or change in existing therapy) or related to a GSK concomitant medication, will be recorded from the time a subject consents to participate in the study up to and including any follow up contact.

The investigators will report life-threatening or fatal unexpected adverse events associated with the use of the study drug or procedures to the DSMB, and the IRB within 24 hours of discovery of the incident with subsequent follow-up submission of a detailed written report.

All SAE will be reported via email notification within 24 hours of awareness to the following sponsor (GSK) contacts including:

- 1) ISS Chairperson
- 2) ISS Managing Director
- 3) GMAL or designee
- 4) LOC Physician
- 5) LOC Safety Contact
- 6) LOC Study Accountable Person
- 7) GCSP Safety Physician
- 8) GCSP Safety Scientist
- 9) [contact]

Serious (but not fatal or life-threatening) and unexpected adverse events associated with the use of the study drugs or procedures must be reported to the DSMB and the IRB within 5 working days with subsequent follow-up submission of a detailed written report.

Adverse Events of Special Interest:

The following adverse events of special interest will be assessed for frequency in the data analyses and final report.

- Serious Hypersensitivity or Infusion Reactions
- Serious infections, including herpes zoster and opportunistic infections
- Malignancy
- Suicidal thought, intent or behaviour

5.6.4 Stopping Rules:

Individual subject-specific stopping rules: A study participant will be discontinued from further study drug treatment/Intervention(s) administration if any of the following occur:

Any clinical adverse event, laboratory abnormality, intercurrent illness, other medical condition or situation occurs such that continued participation in the study would not be in the best interest of the participant.

An unexpected fatal or life-threatening adverse event, which requires discontinuation of study treatment.

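### Subjects terminated early for illness have no stated late adverse-event contact, although the AE comparison makes no stated allowance for follow-up time

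*Combined protocol and SAP*

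**What the plan says.** **Termination.** Section 5.6.4 introduces its subject-level rules as rules for stopping study drug. Two of them go further and end participation in the trial: an exacerbation that leads to extra lung medication or a hospital stay, and any new condition that would have been an exclusion criterion.

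**Follow-up after removal.** Section 2.6 says: "Patients removed from the study for unacceptable AE will be followed until resolution or stabilization of the problem(s". Section 5.6.2 adds that any subject with an AE, related or not, is watched until its outcome is known, if necessary past the observation period. Liver stopping events have their own monitoring.

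**Scheduled contacts.** Table 2 and section 2.6.2 set all contacts by study day: a call the day after each infusion, a visit on day 210, a call on day 240, and a last contact on day 300. That last contact is a clinic visit with pregnancy test for women of childbearing potential and a call for everyone else. Section 2.6 gives the detection of late complications as the purpose of the telephone interviews.

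**AE window.** Section 5.6.3 states: "AEs will be collected from the start of study treatment and until the follow up contact". It gives that contact no day.

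**Analysis.** Section 2.8.2 compares the proportion of subjects with AEs by Fisher's exact test and the AE count per subject by exact Poisson tests. Section 6.7.1 plans no imputation of missing safety data.

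**Withdrawals.** The synopsis says that "twenty-five subjects will be randomized to account for subjects who have been withdrawn early".

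**Contraception period and windows.** For women of childbearing potential, section 3.2 requires contraception "during the study, and 16 weeks after the last dose of study agent". Section 2.6.3 gives treatments and visits plus or minus 5 days, then states: "A variance of 10 days will be allowed for the surveillance visits on day 210, and day 300 (if applicable". No sign is attached to the 10 days.

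**The concern.** The protocol treats active detection of late events as necessary, because it schedules calls for that purpose after the last infusion. It does not say that these calls continue for a subject who has been terminated. The text on removed subjects covers problems already known, and following a known problem does not find a new infection.

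This matters for three reasons. AE comparison is a secondary endpoint, and section 5.6.3 lists serious infections, malignancy and suicidality as events of special interest. Termination is triggered by illness, so the subjects who may leave active ascertainment are plausibly at higher risk of later events. The study-wide stopping rule in section 5.6.4 also compares serious AE rates between arms. If removals differ by arm, the arm with more of them may be observed less, and its later events would be under-counted.

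**Working it through.** **1. The plan's own timing.** The last infusion is on day 180 and the last contact on day 300. 300 / 30 = 10 months, which matches the stated ten-month participation and "The final dose is administered at month 6 with final assessment at month 7 and a safety visit at month 10". For a completer on schedule:
- day-240 call: 240 − 180 = 60 days after the last dose
- day-300 contact: 300 − 180 = 120 days after the last dose

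**2. What is stated for a terminated subject.**

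| | Completer | Dosed, terminated early |
|---|---|---|
| Call the day after each infusion | yes | yes, for infusions received |
| Known AE followed to outcome | yes | yes |
| Day-240 AE call | yes | not stated |
| Day-300 AE contact | yes | not stated |
| End of AE collection | day 300 by implication | undefined |

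**3. Is counting from treatment start the cause?** Suppose the existing calls were kept after early stopping.

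| Last dose on day | 1 | 14 | 30 | 60 | 90 | 120 | 150 |
|---|---|---|---|---|---|---|---|
| Days to day-240 call | 239 | 226 | 210 | 180 | 150 | 120 | 90 |
| Days to day-300 contact | 299 | 286 | 270 | 240 | 210 | 180 | 150 |

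Every value exceeds the completer's 60 and 120 days. The anchor is not the fault. The gap is that the plan does not say whether the calls continue.

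**4. What this does to the count comparison (illustration).** Assume a subject has the day-60 infusion, is terminated before the next visit, and is not asked about new events after that. Active observation then ends between the day-61 call and day 90. That is 61/300 = 20% to 90/300 = 30% of the completer's calendar window. No exposure term is stated for the Poisson comparison, so on the text as written this subject's count is compared as if the window were full.

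**5. How many subjects.** 25 − 18 = 7, and 7/25 = 28%. This is an upper figure for early withdrawals of every kind. The synopsis attributes them to pandemic restrictions and to medical reasons unrelated to study drug or procedures, and it does not say that all were dosed.

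**6. Secondary point: the 16-week period for women of childbearing potential.** 16 × 7 = 112 days.
- On schedule: 120 days, which is 8 more than 112.
- Dose 8 with its ±5-day window falls on days 175 to 185.
- Day-300 variance read as ±10: visit on days 290 to 310. Minimum gap 290 − 185 = 105 days, 7 short of 112; maximum 310 − 175 = 135. A shortfall needs the late dose and early visit together to use more than 8 days, which happens in 28 of 231 whole-day combinations (a count of allowed combinations, not a probability).
- Day-300 variance read as later only: minimum gap 300 − 185 = 115 days, no shortfall.
- Women terminated early: for a last dose at infusions 1 to 7, 112 days ends on day 113, 126, 142, 172, 202, 232 or 262. No pregnancy test is stated for that period after termination.

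**The case against.** The strongest reply is that nothing limits the late calls to completers. The sentence after the quoted line in section 2.6 promises telephone interviews for late complications, and Table 2 excludes no one. Section 2.7.2 accepts AEs from contacts started by either side at any time, and section 5.4.2 provides a wallet card, encourages family reports and gives treating physicians access to the investigators. On this view one clarifying line is enough.

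Part of this stands: the defect is silence, not a stated exclusion. But section 5.6.4 removes these subjects from the trial rather than only from drug, and a coordinator could reasonably read that as ending scheduled contacts. Spontaneous reporting is passive, whereas completers are actively called.

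Several stronger readings a reader might draw do not hold:
- **Terminated subjects have no follow-up.** Next-day calls and follow-up of known AEs are stated.
- **The proportion of subjects with any AE is understated.** A subject removed for a recorded AE already counts in it. The exposure lies in counts and in specific later events.
- **28% is the rate of illness-driven removal.** The synopsis does not support that.
- **Sixteen weeks is a general safety period.** It appears only as a contraception and abstinence condition for women of childbearing potential.
- **Completers end before 16 weeks.** On schedule they do not. A shortfall needs window extremes and a ± reading of an unsigned variance. The synopsis prints the day-210 window with a plus sign, which may be a misread ±, so the sign cannot be settled from the text.

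**Conclusion.** The point holds for dosed subjects terminated early. Read as written, the plan schedules nothing after the next-day call to find new late events in them, while completers are contacted 60 and 120 days after their last dose. A stated, illness-triggered termination rule feeds into AE comparisons with no stated allowance for follow-up time, so this is more than a missing detail.

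The direction is conditional: AE counts and specific later events can be under-ascertained in whichever arm has more removals. The size cannot be computed from the documents. At most 7 of 25 randomised subjects are implied as early withdrawals, and those both dosed and removed for illness may be fewer. The conclusion assumes that termination from the study is taken to end scheduled contacts.

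The contraception-window point is minor. The gap can be 105 days against 112, only for women of childbearing potential and only if the day-300 variance runs both ways.

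**What to change.** In sections 2.6.2, 5.6.3 and 5.6.4:
1. Separate stopping study drug from leaving AE follow-up.
2. State that every subject who received study drug, including those terminated, keeps the existing late AE contacts over the same calendar window as completers unless consent is withdrawn.
3. Define the follow-up contact that closes AE collection accordingly.

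Keeping the calendar window is preferable to ending AE collection a fixed time after the last dose. With a 16-week cut-off, a subject who stopped after the first infusion would leave observation near day 113 while completers continue to day 300, which would build the unequal observation into the plan.

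Secondary: give the sign of the day-300 variance in section 2.6.3. Reconcile it, together with the ±5-day dose window, with the 16-week contraception period, and reconcile how that period is covered for women terminated early.

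Cost: about two phone calls in the existing format per terminated subject. Some will decline, so some loss will remain.
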